4.3.1.2. Main analytical approach

All secondary PK analyses will be based on the PK Analysis Set. PK analysis will be the responsibility of Clinical Pharmacology Modelling and Simulation (CPMS), GSK. Statistical analysis of the derived PK parameter data will be the responsibility of Clinical Statistics, GSK.

Plasma GSK3965193 concentration-time data will be analyzed by non-compartmental methods. Calculations for the final analysis will be based on the actual sampling time points recorded during the study. The various analyses will be conducted as permitted by data available.

For the calculation of the area under the concentration-time curve (AUC), the linear trapezoidal method will be employed for all incremental trapezoids arising from increasing concentrations and the logarithmic trapezoidal method will be used for those arising from decreasing concentrations (i.e., Linear Up/Log Down calculation method). A

minimum number of three data points (not including Cmax) should be used in calculating λ_z .

Unless otherwise specified, all PK analysis for GSK3965193 will be reported using PK set. PD analysis for GSK3965193 will be reported using PD set.

Safety, PK and PD of Bepirovirsen will be reported using the OBE set. These outputs will only be produced if more than 5 participants choose to take part in the optional Bepirovirsen extension arm.

4.3.1.2.1. Pharmacokinetic Analysis

PK parameters to be analyzed are listed below in [Table 7](#).

Table 7 List of Pharmacokinetic parameters

PK Parameter	Parameter Description
Cmax	Maximum observed concentration, determined directly from the concentration-time data
Tmax	Time to reach Cmax, determined directly from the concentration-time
AUC _(0-tau)	Area under the concentration-time curve (CCI [REDACTED] (CCI [REDACTED]) using, the linear trapezoidal rule for each incremental trapezoid and the loge trapezoidal rule for each decremental trapezoid (linear up/log down calculation method in Phoenix WinNonlin).
Ctrough	Trough Concentration (CCI [REDACTED])
Terminal Half-life T _{1/2}	Apparent terminal half-life will be calculated after first dosing (CCI [REDACTED]) and last dose (CCI [REDACTED]): $t_{1/2} = \ln 2 / \lambda_z$ 
Note: λ_z is terminal phase rate constant

PK concentrations sampled outside the PK sampling windows will be included in listings and in subject level figures but will not be included in summaries.

AUC_(0-tau), Cmax, and Ctrough will be summarized by timepoint based on the log-transformed data. Tmax and t_{1/2} will be summarized by treatment and timepoint as applicable based on untransformed data.

The following figures will be produced:

- A by-participant graph of the concentration data over time, on linear and semilogarithmic scales
- Mean and median concentration +/- CI will be plotted on linear and semilogarithmic scales.

A by-participant listing of pharmacokinetic concentration values at each time point will be produced. All PK parameters will also be listed.

Model analysis for PK endpoints –

Table 8 Model Analysis Specification for Steady State

Endpoint(s)	

 Ctrough 	
Analysis Method	

 Frequentist approach, Analysis of Variance 	
Model Specification and Analysis for different parameters	
Steady State Analysis	
Steady state will be assessed by analysing log_e transformed trough plasma concentration using Mixed Model with the following effects:
 
 Fixed effect: Day Random effect: Subject 
An unstructured covariance matrix will be considered for the G matrix describing the between subject variability. If this model fails to converge, alternative covariance structures may be considered such as Variance Component, Compound Symmetry, etc. Akaike's Information Criteria (AIC) will be used to assist with the selection of covariance structure.
 
The Kenwood and Roger method for approximating the denominator degrees of freedom and correcting for bias in the estimated variance-covariance of the fixed effects will be used.
 
Distributional assumptions underlying the model used for analysis will be examined by obtaining a normal probability plot of the residuals and a plot of the residuals versus the fitted values (i.e., checking the normality assumption and constant variance assumption of the model respectively) to gain confidence that the model assumptions are reasonable.
 
The coefficients of the slopes for the day CCI effect on log scale for each dose, along with 90% CI, will be used to determine whether steady state was achieved.

4.3.1.2.2. Pharmacodynamic Analysis

HBsAg will be collected CCI
GSK3965193 treatment period. Again, HBsAg will be collected from CCI
CCI

Individual line plot will be provided for change from baseline for HBsAg levels
GSK3965193 and Placebo CCI

Following summaries will be provided -

- Proportion of PLWCHB who achieved HBsAg $\geq 0.5 \log_{10}$ IU/mL decline and/or <LLOQ in HBsAg at any Visit during the Treatment

CCI

4.3.1.2.3. Adverse events, Serious Adverse events, and Adverse Event of Special Interest (AESI)

An AE is considered study treatment emergent if the AE onset date or worsen date is on or after study treatment start date.

For this part and for optional Bepirovirsen arm TEAE will be derived as following -

- TEAE for Bepirovirsen = Date of First Bepirovirsen Dose \leq Date of AE Onset/Worsening

All AE summaries will be based on treatment emergent events and summarised by treatment. SAE summaries will also be based on treatment emergent SAEs. All non-treatment emergent AEs and SAEs will be listed. The following displays for Adverse events will be generated:

Table 10 Adverse event summary table for optional Bepirovirsen

	Optional Bepirovirsen Arm
AEs	Overview of all Adverse Events
	Summary of Treatment Emergent Adverse Events by System Organ Class and Preferred Term
	Summary of Treatment Emergent Adverse Events Leading to Treatment Discontinuation by System Organ Class and Preferred Term
	Summary of Treatment Emergent Adverse Events by System Organ Class and Preferred Term and Maximum Grade
	Summary of Treatment Emergent Drug-Related Adverse Events by System Organ Class and Preferred Term and Maximum Grade

	Optional Bepirovirsen Arm
	Summary of Treatment Emergent Common ($\geq 10\%$) Non-Serious Drug-Related Treatment Emergent Adverse Events by Overall Frequency
	Summary of Treatment Emergent Non-serious Adverse Events by System Organ Class and Preferred Term (Number of Subjects and Occurrences)
SAEs	Summary of Treatment Emergent Serious Adverse Events by System Organ Class and Preferred Term and Maximum Grade
	Summary of Treatment Emergent Serious Adverse Events Leading to Treatment Discontinuation by System Organ Class and Preferred Term
	Summary of Treatment Emergent Serious Fatal and Non-Fatal Drug-Related Adverse Events by Overall Frequency
	Summary of Treatment Emergent Serious Adverse Events by System Organ Class and Preferred Term (Number of Participants and Occurrences)
	Summary of Deaths
AESI	Summary of Adverse Events related to ALT increase by System Organ Class and Preferred Term
	Summary of Adverse Events related to vascular inflammation and complement activation by System Organ Class and Preferred Term
	Summary of Adverse Events related to thrombocytopenia by System Organ Class and Preferred Term
	Summary of Adverse Events related to renal injury by System Organ Class and Preferred Term
	Summary of Adverse Events related to injection site reaction by System Organ Class and Preferred Term
	Summary of Adverse Events related to Neuropathy Events by System Organ Class and Preferred Term
	Summary of Adverse Events related to Neurocognitive Events by System Organ Class and Preferred Term

4.3.1.2.4. Laboratory Data, and Vital Sign

For laboratory data (haematology, clinical chemistry, urinalysis) and vital signs data, the following will be summarized:

1. For selected parameters, values outside the PCI range at each visit will be summarized as clinically significant. All other parameters will be summarized based on normal range values.
2. Change from baseline values at each visit.

Laboratory parameters will be graded using [DAIDS, 2017] Table for Grading the Severity of Adult and Paediatric Adverse Events Version 2.1.

CCI [REDACTED]

CCI [REDACTED]

CCI [REDACTED]

CCI [REDACTED]

CCI [REDACTED]

CCI [REDACTED]

CCI [REDACTED]

CCI [REDACTED]

CCI [REDACTED]

CCI [REDACTED]

CCI [REDACTED]

CCI [REDACTED]

CCI [REDACTED]

CCI [REDACTED]

CCI [REDACTED]

CCI [REDACTED]

CCI [REDACTED]

CCI [REDACTED]

CCI [REDACTED]

CCI [REDACTED]

CCI [REDACTED]

CCI [REDACTED]

CCI [REDACTED]

CCI [REDACTED]

CCI [REDACTED]

CCI [REDACTED]

CCI [REDACTED]

CCI [REDACTED]

CCI [REDACTED]

CCI [REDACTED]

CCI [REDACTED]

CCI [REDACTED]

CCI

CCI

CCI

CCI

CCI

CCI

CCI

4.5. Other Safety Analyses

The safety analyses will be based on the Safety Set for GSK3965193, and OBE set for Optional Bepirovirsen arm, unless otherwise specified.

4.5.1. Extent of Exposure

Extent of exposure to study intervention will be summarized. The number of days of exposure to study treatment (GSK3965193/Placebo) will be calculated based on the formula given below:

Duration of Exposure (in Days) = (Treatment Stop Date – Treatment Start Date) + 1

Participants who were randomized but did not report a treatment start date will be categorized as having zero days of exposure. The cumulative dose will be based on the formula:

Cumulative Dose = Sum of (Number of Exposure Days x Total Daily Dose)

Optional Bepirovirsen arm will be using 300mg Bepirovirsen Subcutaneous (SC) weekly dose until week 24 weekly, plus additional 300mg loading doses in weeks 1 and 2.

Number of participants with < 6 weeks, <=12 weeks, <=24 weeks exposure and > 24 weeks exposure will be presented, and overall duration will be summarized.

Number of days of exposure to study drug will be calculated based on the formula below:
Duration of Exposure in Days = Last injection date – First injection date + 1

The cumulative dose will be based on the formula below:

Cumulative Dose = Number of Injections of 300mg x 300mg + Number of Loading doses x 300mg.

In case of temporary treatment hold for 1 or more than 1 day, for both GSK3965193 and for optional bepirovirsen arm, the following formula will be used for calculation of “Duration of Exposure”.

Duration of Actual Exposure (in Days) = (Treatment Stop Date – Treatment Start Date + 1) – Number of days treatment on hold.

4.6. Other Analyses

4.6.1. Subgroup analyses

Not Applicable

4.6.2. Other variables and/or parameters

Not applicable.

4.7. Interim Analyses

In Part 3, CCI [REDACTED]
 CCI [REDACTED]
 CCI [REDACTED]
 CCI [REDACTED]
 CCI [REDACTED]
 CCI [REDACTED]
 CCI [REDACTED]

Details of all interim analyses will be described in the Part 3 Interim Analysis Charter.

4.8. Changes to Protocol Defined Analyses

Changes from the originally planned statistical analysis specified in the protocol are detailed in [Table 12](#).

Table 12 Changes to Protocol Defined Analysis Plan

Protocol Defined Analysis	SAP Defined Analysis	Rationale for Changes

 Endpoints for Bepirovirsen optional arm 	
 Cardiac and ECG assessments have not been documented in SAP for Bepirovirsen Optional arm 	
 Cardiac assessment for Bepirovirsen arm has been removed as a secondary objective since cardiac assessment endpoint was incorrectly included in the protocol, and the data is not being collected on the database.

 Definition of Analysis Sets 	
 Definition of PD Analysis Set has been updated to remove any participant who takes a prohibited medication (as per the protocol) pre-treatment. 	
 CCI [REDACTED] CCI [REDACTED] CCI [REDACTED] CCI [REDACTED] CCI [REDACTED] CCI [REDACTED] CCI [REDACTED] There was a need to define an additional analysis population to

Protocol Defined Analysis	SAP Defined Analysis	Rationale for Changes
	
 An additional analysis set, Bepirovirsen Extension (OBE) set has been defined 	
evaluate participants who choose to take part in the optional Bepirovirsen arm

 Estimand 	
 Primary estimand and secondary estimand has been re-defined (clinical question, estimand policy strategy, and estimation of estimand) in Section 1.1.1 and Section 1.1.2 . Also, Supplementary estimand added in Section 1.1.3 as per the suggestion of Estimand SME group. 	
 Following clinical discussion, the estimand framework was updated to align with best practice.

5. SAMPLE SIZE DETERMINATION

CCI [REDACTED]

CCI [REDACTED]

CCI [REDACTED]

CCI [REDACTED]

CCI [REDACTED]

CCI [REDACTED]

CCI [REDACTED]

CCI [REDACTED]

CCI [REDACTED]

CCI [REDACTED]

CCI [REDACTED]

CCI [REDACTED]

CCI [REDACTED]

CCI [REDACTED]

CCI [REDACTED]

CCI [REDACTED]

CCI
CCI
CCI
CCI

6. SUPPORTING DOCUMENTATION

6.1. Appendix 1 Study Population Analyses

Unless otherwise specified, the study population analyses for GSK3965193 vs Placebo part of the study will be based on the Safety Set and optional Bepirovirsen arm will be using Optional Bepirovirsen Extension set. A summary of the number of participants in each of the participant level analysis set will be provided.

This is a multicenter global study; enrolment will be presented by country and site.

6.1.1. Participant Disposition

A summary of the number and percentage of participants who completed the study as well as those who prematurely withdrew from the study will be provided. Reasons for study withdrawal will be summarized. For those who have neither completed nor withdrawn, they will be categorized as on study intervention or in follow up.

A summary of study intervention status will be provided. This display will show the number and percentage of participants who have completed the scheduled study intervention, are ongoing with study intervention, or have discontinued study intervention prematurely, as well as primary reasons for discontinuation of study intervention.

6.1.2. Demographic and Baseline Characteristics

The demographic characteristics including age, gender, ethnicity, height/weight at screening and race will be summarized with descriptive statistics. In addition, the following age categories 18-33, 34-49, 50-65 and HBsAg categories at screening will be also presented for GSK3965193 monotherapy arm. Demographic data will be summarized using Safety Analysis Set.

For Optional Bepirovirsen Extension arm demographic characteristics including sex, age, ethnicity, race, height, and weight will be summarized with descriptive statistics using OBE set. Hepatitis B characteristics, as collected on the Hepatitis B Disease Characteristics eCRF, will be summarized using descriptive statistics and will be listed.

Past medical conditions and current medical conditions as of screening will be summarized respectively.

6.1.3. Protocol Deviations

Important protocol deviations will be summarized.

Protocol deviations will be tracked by the study team throughout the conduct of the study. These protocol deviations will be reviewed to identify those considered as important as follows:

- Data will be reviewed prior to unblinding and freezing the database to ensure all important deviations (where possible without knowing the study intervention details) are captured and categorized in the protocol deviations dataset.
- This dataset will be the basis for the summaries of important protocol deviations.

6.1.4. Prior and Concomitant Medications

Concomitant medications will be coded using WHO Drug dictionaries. However, the summary will be based on WHO Drug dictionary only. The summary of concomitant medications will be provided by ingredient, i.e. multi-ingredient medications will be summarized for each individual ingredient rather than a combination of ingredients. The summary will be created using ingredient base names, i.e. ingredients with the same base name but different salt will appear under one base name in the summary.

6.1.5. Study Intervention Compliance

A summary of overall compliance based on the exposure data will be produced. Overall compliance will be summarized using descriptive statistics as well as

the categories <75%, 75%-100%, and >100%.

Compliance will be summarized both in terms of number of tablets/injections consumed and total dose received during the planned on-treatment period.

- Study intervention Compliance (%) = [Number of actual doses / Number of planned doses] * 100.
- Study dose Compliance (%) = [Actual Total Dose / Planned Total Dose] * 100

6.2. Appendix 2 Data Derivations Rule

6.2.1. Criteria for Potential Clinical Importance

Laboratory test values will be considered of potential clinical importance if they fall outside the specified PCI ranges provided in the table compared to the baseline values.

Reference ranges for all laboratory parameters collected throughout the study are provided by the laboratory. A laboratory value that is outside the reference range is considered either high abnormal or low abnormal.

Grading categories for laboratory tests are determined using the [DAIDS, 2017] grading system Version 2.1.

Table 14 List of PCI Ranges for selected Laboratory Parameters

Analyte	Unit	PCI Range
ALT	IU/L	>2XULN
Albumin	g/dL	≤3.5
Glomerular filtration rate (GFR)	mL/min /1.73m ²	≤60
INR		>1.25
Platelet count	x 10 ⁹ /L	<140
Total bilirubin	umol/L	>1.25 x ULN

Table 15 List of PCI Ranges for ECG Parameters

ECG Parameters	Unit	PCI Range	
		Lower(<x)	Upper(>x)
Absolute QTc	msec	300	450
Absolute QTcF	msec	300	450
Uncorrected QT	msec	N/A	600
Heart rate	bpm	50	110
Absolute QRS interval	msec	70	120
Absolute PR Interval	msec	90	220
Change from Baseline:			
QTcF	msec	>60	

Table 16 List of PCI Ranges for Vital Sign Parameters

Vital Parameters	Unit	PCI Range	
		Lower(<x)	Upper(>x)
Pulse rate	bpm	50	110
Respiratory Rate	Breaths/min	8	20
Systolic blood pressure	mmHg	85	160
Diastolic Blood Pressure	mmHg	45	100

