**5.1.3. Additional Inclusion Criteria for PLWCHB (Parts 3 and 4)**

TYPE OF PARTICIPANT AND DISEASE CHARACTERISTICS	
6.	Participants who have documented chronic HBV infection $\geq 6$ months prior to screening
7.	Participants currently receiving stable nucleos(t)ide analog (NA) therapy (e.g., tenofovir disoproxil, tenofovir alafenamide, entecavir). "Stable" is defined as no changes to the nucleos(t)ide regimen for at least 6 months prior to screening and with no planned changes to the regimen for the duration of the study
8.	Plasma or serum HBsAg concentration $> 100$ IU/mL
9.	Plasma or serum HBV DNA concentration $< 90$ IU/mL
10.	HBeAg positive or negative
11.	ALT $\leq 2$ x the upper limit of normal (ULN)

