## 46. Laboratory results as follows:

- a. Serum albumin  $\leq 3.5$  g/dL
- b. Glomerular filtration rate (GFR)  $\leq 60$  mL/min /1.73m^2 as calculated by the chronic kidney diseases epidemiology collaboration (2021 CKD-EPI) formula
- c. INR  $> 1.25$
- d. Platelet count  $< 140 \times 10^9$  /L
- e. Total bilirubin  $> 1.25 \times$  ULN
- f. Urine ACR  $\geq 0.03$  mg/mg (or  $\geq 30$  mg/g). In the event of an ACR above this threshold, eligibility may be confirmed by a second measurement.

**NOTE:** In cases where participants have low urine albumin and low urine creatinine levels resulting in a urine ACR calculation  $\geq 0.03$  mg/mg, the investigator should confirm that the participant does not have a history of diabetes, hypertension or other risk factors that may affect renal function.

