1.1. Objectives, Estimands and Endpoints

Objectives	Endpoints
Part 3 and Part 4 (participants living with chronic hepatitis B infection [PLWCHB])	
Primary	

 To assess the safety and tolerability of oral administration of GSK3965193 monotherapy (Part 3) and in combination with bepirovirsen (Part 4) 	
 Incidence of AEs, SAEs, withdrawals due to AEs Incidence of clinically significant laboratory parameters (haematology, clinical chemistry, urinalysis), vital signs, cardiac parameters (electrocardiogram), and sensory nerve conduction

 To evaluate pharmacodynamic (PD) effect of GSK3965193 monotherapy in PLWCHB (Part 3) 	
 Maximum reduction of serum HBsAg levels from baseline CCI [REDACTED] CCI [REDACTED] CCI [REDACTED]
Secondary	

 To evaluate the PK characteristics of repeat doses of GSK3965193 in PLWCHB (Part 3) 	
 AUC(0-tau), Cmax, Tmax, and apparent terminal half-life (T1/2) will be calculated as data permits

 To evaluate pharmacodynamic (PD) effect of GSK3965193 monotherapy in PLWCHB (Part 3) 	
 ≥0.5x log IU/mL reduction of serum HBsAg levels from baseline anytime during the study (on-treatment and post-treatment)

 To assess the safety and tolerability of bepirovirsen monotherapy in PLWCHB who have completed GSK3965193/placebo monotherapy (Part 3) 	
 Incidence of AEs, SAEs, withdrawals due to AEs Incidence of clinically significant laboratory parameters (haematology, clinical chemistry, urinalysis), vital signs
Exploratory	

CCI

Objectives	Endpoints
CCI	

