4.2.1. Definition of endpoints

The following endpoints will be assessed:

- Occurrence of AEs and SAEs
- Occurrence of clinically significant changes in laboratory values (hematology, clinical chemistry, and urinalysis), vital sign parameters, 12-lead ECG parameters, and sensory nerve conduction parameters
- Maximum reduction of HBsAg levels from baseline CCI

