4.2.2.2. Laboratory Data, Vital Signs and ECG Data

For laboratory (haematology, clinical chemistry, urinalysis), vital signs, and ECG data, the following will be summarized:

1. For selected parameters, values outside the Potential Clinical Importance (PCI) range at each visit will be summarized as clinically significant. All other parameters will be summarized based on normal range values.
2. Change from baseline values at each visit.

Additional ECG summaries:

- Summary of Maximum QTc Values Post-Baseline Relative to Baseline by Category
- Summary of Maximum Increase in QTc Values Post-Baseline Relative to Baseline by Category

Laboratory parameters will be graded using [DAIDS, 2017] grading system Version 2.1, Table for Grading the Severity of Adult and Paediatric Adverse Events.

RAPIDO listings will be generated for the laboratory parameters.

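### The Part 3 SAP flags laboratory values outside the PCI range, but Table 14 lists the abnormal region for its six analytes, so the rule as worded is inverted

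*SAP*

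**What the plan says.** Three places in the Part 3 SAP give the same rule.

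- Section 6.2.1 says laboratory values are of potential clinical importance "if they fall outside the specified PCI ranges provided in the table compared to the baseline values".
- Section 4.2.2.2 (GSK3965193 versus placebo) covers laboratory, vital sign and ECG data together. For selected parameters, "values outside the Potential Clinical Importance (PCI) range at each visit will be summarized as clinically significant".
- Section 4.3.1.2.4 (optional bepirovirsen extension) repeats this for laboratory data and vital signs: "values outside the PCI range at each visit will be summarized as clinically significant".

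In both analysis sections, parameters that are not selected are summarised against their normal ranges.

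Table 14 has one column, headed as the PCI range, with a single inequality per analyte. Tables 15 and 16 have a lower and an upper limit for each parameter, and their column heads carry the operator. The exception is the QTcF change-from-baseline row of Table 15, which has a single entry of >60 msec.

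The flag feeds the Part 3 primary safety endpoint, given in section 1.1 as "Incidence of clinically significant laboratory parameters (haematology, clinical chemistry, urinalysis), vital signs, cardiac parameters (electrocardiogram), and sensory nerve conduction" and restated in section 4.2.1. For the extension it feeds a secondary safety endpoint (sections 1.1 and 4.3.1.1).

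**The concern.** A derivation rule should let two programmers produce the same flag without guessing. Here one word, outside, is applied to two table formats. With a lower and an upper limit, outside means abnormal. With the one-sided inequalities of Table 14, which describe the abnormal region, outside means the normal side. The next paragraph of 6.2.1 adds to the difficulty by using the same word, correctly, for results beyond the laboratory's reference range.

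If the flag were programmed or quality-checked to the letter, the displays of clinically significant laboratory values would count unremarkable results for these six analytes and omit the abnormal ones. Four of the six (ALT, total bilirubin, platelets and GFR) bear directly on the liver, platelet and renal risks that protocol section 2.3.1 lists for bepirovirsen.

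**Working it through.** The plan states no figure to reproduce. The check is to set the rule beside the table and the entry criteria, and then apply it to example values.

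**Step 1. Table 14 against the entry limits** (protocol section 5.1.3, criterion 11, for ALT; section 5.2.2, criterion 46, for the rest)

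| Analyte | Table 14 entry | Protocol entry rule | Side listed in Table 14 |
|---|---|---|---|
| ALT | >2xULN | included only if ≤2xULN | abnormal |
| Albumin, g/dL | ≤3.5 | excluded if ≤3.5 | abnormal |
| GFR, mL/min/1.73m² | ≤60 | excluded if ≤60 | abnormal |
| INR | >1.25 | excluded if >1.25 | abnormal |
| Platelets, x10⁹/L | <140 | excluded if <140 | abnormal |
| Total bilirubin | >1.25xULN | excluded if >1.25xULN | abnormal |

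Five rows equal an exclusion limit, and the ALT row is the complement of the inclusion limit. The operators are therefore deliberate and mark values that would bar entry.

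**Step 2. The two readings**

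- As written: flag = value is not in the Table 14 region.
- As evidently intended: flag = value is in the Table 14 region.

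**Step 3. Example values.** These are assumed for illustration: one normal, one at or just inside the entry limit, and one abnormal per analyte, so 6 x 3 = 18.

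| Analyte | Normal | Entry limit | Abnormal | Flagged as written | Flagged as intended |
|---|---|---|---|---|---|
| ALT (xULN) | 0.8 | 2.0 | 5.0 | 0.8, 2.0 | 5.0 |
| Albumin | 4.2 | 3.6 | 2.8 | 4.2, 3.6 | 2.8 |
| GFR | 95 | 61 | 40 | 95, 61 | 40 |
| INR | 1.0 | 1.25 | 1.8 | 1.0, 1.25 | 1.8 |
| Platelets | 220 | 140 | 70 | 220, 140 | 70 |
| Bilirubin (xULN) | 0.6 | 1.25 | 3.0 | 0.6, 1.25 | 3.0 |

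As written, 6 x 2 = 12 of 18 values are flagged and none of the 6 abnormal ones. As intended, 6 of 18 are flagged, exactly the abnormal ones. The split follows from the inequalities and is not an estimate of any rate in the trial.

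**Step 4. Consequence at entry.** Every eligible participant lies outside all six regions at the values used to qualify, so the literal rule would flag all six analytes at those values in both arms. A participant whose ALT then rose above 2xULN would lose the ALT flag.

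**Step 5. The other tables.** For the lower/upper rows of Tables 15 and 16, outside gives the right direction. The QTcF change row is weaker evidence. The 6.2.1 sentence speaks only of laboratory tests, so the rule reaches ECG through 4.2.2.2. It is also not certain, in the text available to me, which column the >60 entry belongs to; under the upper column it would merely repeat the operator.

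**Step 6. The baseline clause.** The 6.2.1 sentence ends by comparing with baseline, but Table 14 holds absolute cut-offs and no comparison is defined. Step 3 therefore could not apply it. If the clause meant that only values that changed region since baseline count, the direction would still be reversed: moving from the abnormal to the normal side would be counted.

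**The case against.** The strongest reply is that this is a drafting slip whose meaning is plain. The column heads of Tables 15 and 16 attach the operator to the flagged direction. Read the same way, Table 14 flags ALT >2xULN, platelets <140 and so on, and one reading serves all three tables. The entry limits confirm it, and a careful programmer would probably code it correctly. This stands, and it limits the point to wording. It does not remove it, because reaching the right flag means going against the written rule in three places and no other text in the SAP corrects it.

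A reader might infer that the primary safety endpoint as a whole ignores abnormal results. The documents do not support that. The endpoint also covers adverse events, vital signs, ECG and nerve conduction. Within the laboratory data only six analytes are involved. Their abnormal values would still appear through DAIDS grading and change from baseline at each visit (4.2.2.2 and 4.3.1.2.4), through listings (4.2.2.2), and through the adverse event tables, since protocol section 8.2.7 has investigators record clinically significant laboratory changes as adverse events. No hypothesis is tested (SAP section 2), and no decision rule visible in the documents uses the flag.

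A reader might also infer 100% incidence at baseline. That does not follow. Entry limits govern the qualifying values, whereas SAP section 4.1.3 takes the laboratory baseline as the later of Day -1 or pre-dose Day 1 and allows unscheduled visits. The extension has its own baseline visit, which is redacted.

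**Conclusion.** The point holds as a contradiction between the rule in 6.2.1, 4.2.2.2 and 4.3.1.2.4 and the content of Table 14. Taken literally, the laboratory PCI flag is reversed for six of six analytes, in the primary safety endpoint and in the secondary safety endpoint of the extension. The QTcF change row may share the problem but should not carry weight.

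The practical harm is conditional: displays would be wrong only if the flag were programmed or checked as written. Nothing in the documents shows that this has happened. The conclusion rests on the Table 14 operators being as printed, which their agreement with the entry criteria supports. It does not question the choice of cut-offs. The wording should be corrected because it defines part of a primary endpoint, but it is not a reason to doubt the rest of the safety analysis.

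**What to change.** In the Part 3 SAP:

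1. Rename the Table 14 column to PCI criterion, and state in 6.2.1 that a laboratory value is flagged when it meets the criterion for its analyte.
2. For the lower/upper rows of Tables 15 and 16, state that a value is flagged when it is below Lower or above Upper. For the QTcF change row, state that it is flagged if >60 msec.
3. Use the same wording in 4.2.2.2 and 4.3.1.2.4.
4. Delete the comparison with baseline from 6.2.1, or define it.

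The cost is SAP text only. No cut-off changes, and no new data or displays are needed. If the flag is already programmed, its direction should be confirmed against the corrected text.
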